## 2.3 Study Duration

Subjects will participate in this study for up to two (2) years. Participants will be followed until hospital discharge and will be seen/contacted by an Investigator and/or study team member for follow up visits at six (6) weeks, three (3) months, six (6) months and 12 months and 24 months. Once a subject has been diagnosed with a true hernia recurrence (either by physical exam or by CT Scan), he/she will be followed only for the planned re-operation (if indicated) and details of the etiology of the recurrence will be captured in the subject's study binder (CRF), when available. The subject will only be followed to capture information about the re-operation once a recurrence is diagnosed.

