## 2.4.2 Secondary Endpoints

- Recurrent hernias (functional hernias) requiring surgical intervention
- True recurrence at 24 months
- Evidence of Eventration/Hernia Recurrence (Radiographic)
- Fluid collection (Seroma, Hematoma)
- Surgical Site Infections
- Systemic Infections
- Enterocutaneous Fistula
- Dehiscence
- Implant failure requiring partial or total removal
- Patient satisfaction (using the SF-36 questionnaire) at Baseline, 3 months, 6 months, 12, and 24 months.
- Days to discharge
- Pain measured using the Visual Analog Scale for discomfort at Baseline, 3 months, 6 months, 12 months, and 24 months.
- Patient contentment with the cosmetic results at 12 months, 24 months and/or at the time of study withdrawal except for patients who have been withdrawn due to recurrence.

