#### 3.2 Statistical Plan

Given the 1:1 randomized nature of the clinical trial and to preserve the inherent characteristics of the randomization, analysis by intention-to-treat (ITT) is chosen. This type of analysis compares the study groups in terms of the treatment to which they were randomly allocated, irrespective of the treatment they actually received or other trial outcomes. Regardless of protocol deviations and participant compliance or withdrawal, analysis is performed according to the assigned treatment group. This type of analysis will also help to demonstrate if there is superiority of one mesh over the other.

If there is no superiority of one mesh over the other, analysis will be performed using the same outcomes to assess if there is equivalence between both meshes. This will demonstrate that there is no clinically significant difference between the two treatment arms.

For statistical analysis, these outcomes can be classified into two measurement scales- continuous and categorical. For continuous outcome, mean and standard deviation, median and range for each group will be calculated. ANOVA will be used to compare the difference in the means among the two groups when data are reasonably normally distributed. Otherwise, non-parametric ANOVA will be used. For categorical data, proportion will be obtained for each outcome, along with 95% CI derived from exact method. Difference in the proportions among the four groups will be compared using Fisher's exact test.

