## 6.7 Visit 7 (12 months Post-Operative +/-28 days):

- 1. General physical examination and surgical site evaluation
- 2. Lateral and frontal photographs performed with subject sitting and standing (when physically capable). For subjects who are not able to position themselves in a specific manner for the photograph due to physical limitations, the reason for this will be recorded in the subject's study record and this will not be considered a protocol deviation
- 3. Adverse events evaluation (graft failure, dehiscence, enterocutaneous fistulas, seromas, wound infection, systemic infections, bleeding, etc.)
- 4. Return to OR for additional repair or graft removal (scheduled or date of return)
- 5. Review Medications (After surgery only medications that could impact healing will be recorded including but not limited to steroids, antibiotics)
- 6. Use of Wound V.A.C.® and reason for use.
- 7. Date(s) of drain(s) removal, reason for drain (s) removal (i.e. drains have been in place for 7 days and/or the 24 hour fluid collection is < 30 cc /day, or any other reason removed).
- 8. Patient Satisfaction form (SF-36)
- 9. Physical evaluation for hernia recurrence

\*\*\*Once a subject has been diagnosed with a true hernia recurrence (either by physical exam or by CT Scan), he/she will be followed only for the planned re-operation (if indicated) and details of the etiology of the recurrence will be captured in the subject's study binder (CRF), when available. The subject will only be followed to capture information about the re-operation once a recurrence is diagnosed.

\*\*\*There is no need to capture implant related data or to conduct follow up visits between the diagnosis of recurrence and the operation for the recurrence. If a participant is not scheduled for a re-operation, his/her study participation will end at this point and this information will be documented on the CRF.

- 10. Clinical evidence of eventration, implant failure, implant related complications, etc. Photographs of the surgical site may be taken to document evidence of adverse events, eventration, implant failure, implant related complications, etc.
- 11. VAS
- 12. Patient contentment with the cosmetic results

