#### **6.10 Schedule of Events:**

## **Schedule of Events**

	Visit 1 Baseline	Visit 2 Surgery	Visit 3 Hospital Discharge (-2 days)	Visit 4 6 Weeks (+/- 1 week)	Visit 5 3 Months (+/- 14 days)	Visit 6 6 Months (+/- 28 days)	Visit 7 12 Months (+/- 28 days)	Visit 8 Telephone 24 Months (+/- 28 days)
Informed Consent	X							
Physical Exam	Х		Х	Х	Х	Х	Х	
Medical, Social, Surgical History	Х	Х						
Medications	X	X	X	X	X	Х	X	X
Adverse Events		X	Χ	X	X	X	X	X
SF36*	X				X	X	X	X
VAS*	X				X	X	X	X
Clinical Evaluation	X		Х	X	X	X	X	
Photographs	Х	Х	Х	Х	Х	Х	х	
Patient Contentment with cosmetic results*							х	х

\*If withdrawn early complete patient contentment cosmetic results.

\*If the subjective questionnaires entitled Visual Analog Scale (VAS), SF-36, and Patient Contentment cannot be completed visually by the subject, for the VAS, patients will be asked to rate their pain on a scale of 1-10. Patients will be asked questions on the SF-36 and Patient Contentment and the answers will be transcribed by designated study staff.

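### Scheduled follow-up stops at a diagnosed true recurrence, so later SF-36, pain and cosmetic scores are missing because of the primary outcome, and any difference that acts through recurrence is diluted toward zero

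*Combined protocol and SAP*

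**What the plan says.** Section 2.3 limits follow-up after a true recurrence to the re-operation and the cause of the recurrence: "The subject will only be followed to capture information about the re-operation once a recurrence is diagnosed". The visit sections (6.3 to 6.7, and 6.9 for unplanned visits) carry the same rule. Section 6.7, for example, does not require sites "to capture implant related data or to conduct follow up visits between the diagnosis of recurrence and the operation for the recurrence", and adds: "If a participant is not scheduled for a re-operation, his/her study participation will end at this point".

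The endpoints concerned are in section 2.4.2:

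- "Patient satisfaction (using the SF-36 questionnaire) at Baseline, 3 months, 6 months, 12, and 24 months"
- "Pain measured using the Visual Analog Scale for discomfort at Baseline, 3 months, 6 months, 12 months, and 24 months"
- Contentment with the cosmetic result at 12 and 24 months and/or "at the time of study withdrawal except for patients who have been withdrawn due to recurrence"

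The footnote to the Schedule of Events (section 6.10) has no such exception: "If withdrawn early complete patient contentment cosmetic results".

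On analysis, sections 3.2 and 3.3 commit to intention-to-treat: "Regardless of protocol deviations and participant compliance or withdrawal, analysis is performed according to the assigned treatment group". Neither section gives a method for missing data, a rule for outcomes after recurrence, or a sensitivity analysis. Both go on to an equivalence assessment on the same endpoints if superiority is not shown.

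On safety, section 7.2 follows adverse events no further than the end of a subject's participation. Section 7.3 requires serious events to be recorded even after follow-up if treatment cannot be ruled out as a cause.

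**The concern.** The protocol itself creates this missingness, and the trigger is the primary outcome. Ordinary dropout may or may not be related to how the patient is doing. Here a score is absent because the repair failed. If the implants differ in recurrence, the number of absent scores also differs by arm for a reason caused by treatment.

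What remains at a later visit is a comparison within a group defined after randomisation: the patients whose repair was still intact. Assigning those patients to their randomised arm does not restore the intention-to-treat comparison. A benefit to pain, quality of life or appearance that works by preventing recurrence cannot show up there. A null result would then feed an equivalence statement.

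Complication rates are part of the stated objective (section 1.2), so the partial loss of later complications matters as well.

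**Working it through.** **No stated figure decides this.** The point concerns data collection. The only design number needed is 60 per arm (section 3.1).

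**What is lost and what is kept after a diagnosed recurrence**

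| Outcome | Status |
|---|---|
| SF-36 and VAS at later visits among 3, 6, 12 and 24 months | Not collected |
| Contentment at later visits (12, 24 months) | Not collected; sections 2.4.2 and 6.10 conflict on the exit rating |
| Forms due at the visit of diagnosis | Not excluded; the text does not say |
| Non-serious complications after diagnosis | Largely lost |
| Complications before diagnosis | Kept |
| Re-operation details and cause of recurrence | Kept (2.3) |
| Later serious events possibly due to treatment | Kept (7.3) |
| Primary endpoint; true recurrence at 24 months; recurrence needing surgery; days to discharge | Unaffected |

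The loss falls mainly at 24 months, and at earlier visits for patients who recur early.

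**How many patients (illustration only).** Section 2.2 cites recurrence of 18 to 50% after incisional hernia repair.

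- 60 × 0.18 = 10.8, about 11 per arm.
- 60 × 0.50 = 30 per arm.
- With the upper planned dropout of 20%, taken as independent of recurrence: 60 × 0.80 = 48 per arm. At 18% v 50% recurrence, 48 × 0.82 = 39.4 and 48 × 0.50 = 24 remain, about 39 v 24.

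These counts treat every recurrence as diagnosed before the visit in question.

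**Effect on the comparison.** Assume that the implant acts on the score only through recurrence, and that recurrent patients score D standard deviations worse. With recurrence p_A and p_B, the difference between all randomised patients is (p_B − p_A) × D against arm B. Among recurrence-free patients it is 0.

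| p_A v p_B | D = 0.25 | D = 0.5 | D = 1.0 | Recurrence-free only |
|---|---|---|---|---|
| 18% v 18% | 0 | 0 | 0 | 0 |
| 18% v 30% | 0.12 × 0.25 = 0.03 SD | 0.06 SD | 0.12 SD | 0 |
| 18% v 50% | 0.32 × 0.25 = 0.08 SD | 0.16 SD | 0.32 SD | 0 |

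In points, with assumed recurrence of 18% v 35% and an assumed 10-point deficit: (0.35 − 0.18) × 10 = 1.7 points among all randomised patients, and 0 among those whose repair held. The rates chosen for each arm and D are assumptions; the documents give neither.

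**The case against.** **The loss is narrower than the rule first suggests.** A reader might infer that nearly every secondary endpoint is lost, or that implant removal after recurrence goes unrecorded. The documents do not support either. Several endpoints are untouched, and most complication items in section 2.4.2 carry no 12- or 24-month time point. The re-operation, where removal of a failed implant would normally be recorded, is exactly what section 2.3 still follows. Section 7.3 covers serious later events possibly due to treatment. SF-36 and VAS are listed at the 3-, 6- and 12-month visits beside the recurrence examination, and section 6.9 suggests them at unplanned visits, so a recurrence first found at month 12 can still contribute that day's scores. All of this stands.

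**The direction is not an advantage for the worse arm.** A reader might infer that the arm with more recurrences will look better. The arithmetic above shows dilution to zero, not reversal. An apparent advantage needs a further assumption: that patients who recur also had poorer underlying scores. With an assumed correlation of 0.3 to 0.5 it would be 0.05 to 0.09 SD at 18% v 30%, or 0.14 to 0.24 SD at 18% v 50%. Nothing in the documents supports that correlation.

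**The size is uncertain and may be small.** The 18 to 50% range names no follow-up time and no implant, and section 1.1 reports lower recurrence with implants, including one porcine-matrix series with none at a mean of 11.1 months. With 60 per arm and an assumed SD of 10 to 25 points, the standard error of a mean difference is SD × √(2/60), or 1.8 to 4.6 points, so a lost difference of 1.7 points is less than one standard error. This stands against any claim of a large effect.

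**Measuring only while the index repair is intact can be defended,** because later scores partly reflect the second repair. That would be a legitimate target if the plan stated it. It does not; it promises the opposite. The equivalence claim also has a separate weakness, since no margin is given.

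**Conclusion.** The point holds in a limited form. Followed as written, the plan makes SF-36, VAS and contentment scores missing because of the primary outcome, chiefly at 24 months and after early recurrences, and it loses most non-serious complications after recurrence. For these endpoints the promised intention-to-treat comparison cannot be carried out on observed data, and no substitute is specified. The two rules on the cosmetic rating at withdrawal contradict each other.

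The expected effect is attenuation toward zero of any difference that acts through recurrence. It requires both unequal recurrence between arms and worse outcomes in recurrent patients. In the illustrations it ranges from 0.03 to 0.32 SD, and the true size cannot be derived from the documents. The primary comparison is not threatened. The change is worth making because it is cheap and because scores that were never collected cannot be recovered by analysis.

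**What to change.** 1. **Collection.** Amend sections 2.3, 6.3 to 6.7 and 6.9 so that, after a recurrence, SF-36, VAS, contentment and complications are still collected at the remaining scheduled time points to month 24, by telephone where needed. Spoken administration already exists in sections 6.8 to 6.10. State that forms due at the visit of diagnosis are completed.
2. **Cosmetic rating.** Reconcile sections 2.4.2 and 6.10 by removing the recurrence exception.
3. **Analysis.** In section 3.2, state that all randomised patients are analysed by assigned arm with post-recurrence scores included. Flag scores taken after re-operation, and include them in the main analysis. Add a sensitivity analysis that handles them differently, for example by giving recurrence the worst rank.

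The cost is a protocol amendment and a few extra contacts per recurrent patient, with travel payment only for scheduled face-to-face visits. Scores after re-operation will partly reflect the second repair; the flag and the sensitivity analysis make that visible but do not remove it. The change concerns data collection, not care.

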#### 2.4 Study Endpoints

## 2.4.1 Primary Endpoints

The primary objective of this study is to compare the incidence of true hernia recurrence (true defect in the implant repair in which intra-abdominal contents are protruding through the defect) at or before 1 year between the Fortiva™ Porcine Dermis group compared with Strattice™ Reconstructive Tissue Matrix group.

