#### 1.2 Rationale

Biologic materials such as Fortiva Porcine Dermis and Strattice Reconstructive Tissue Matrix were developed to provide reinforcement of hernia repair. However, limited high quality prospective data exists on the use of these materials in complex abdominal wall reconstruction, and no comparative data exists. Therefore the objective of this study is to compare the effectiveness of Fortiva Porcine Dermis versus Strattice Reconstructive Tissue Matrix for the underlay reinforcement of complicated ventral hernia repair and assess post-operative complication rates, long term hernia recurrence rates.

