# 5.3.3 Subject Withdrawal and Discontinuation

Subjects may withdraw consent to participate at any time during the study for any reason. The Investigator may also withdraw a subject from the study if the subject:

- i. Is in deviation of the protocol
- ii. Experiences a serious or intolerable AE
- iii. Develops symptoms or conditions listed in the exclusion criteria during the course of the study
- iv. Requests an early discontinuation for any reason

Information regarding all withdrawn or lost-to-follow-up subjects will be documented on the Study Disposition Form. Patients will either complete all the necessary study requirements or their participation in the study may prematurely end for one or more reasons. Patients will be considered "Withdrawn" due to: death, a concurrent illness that prohibits continued participation, the Investigator elects to withdraw the participant due to reasons listed above or because he/she voluntarily withdraws consent at any time during the study for any reason. Such withdrawals shall be documented on the Study Disposition Form. All available information concerning death or concurrent illness should be documented and evaluated for adverse event reporting. If the participant withdraws his/her consent, he/she should be asked (when possible and without coercion) the reason for the decision and notified that data already collected will continue to be

part of the study as per the consent form he/she signed at the time of enrollment. No further study procedures will take place after the participant requests to be withdrawn from the study.

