## 6.6 Visit 6 (6 months Post-Operative +/-28 days):

- 1. General physical examination and surgical site evaluation
- 2. Lateral and frontal photographs performed with subject sitting and standing (when physically capable). For subjects who are not able to position themselves in a specific manner for the photograph due to physical limitations, the reason for this will be recorded in the subject's study record and this will not be considered a protocol deviation
- 3. Adverse events evaluation (graft failure, dehiscence, enterocutaneous fistulas, seromas, wound infection, systemic infections, bleeding, etc.)

- 4. Return to OR for additional repair or graft removal (scheduled or date of return)
- 5. Review Medications (After surgery only medications that could impact healing will be recorded including but not limited to steroids, antibiotics)
- 6. Use of Wound V.A.C. and reason for use.
- 7. Date(s) of drain(s) removal, reason for drain (s) removal (i.e. drains have been in place for 7 days and/or the 24 hour fluid collection is < 30 cc /day, or any other reason removed).
- 8. Patient Satisfaction form (SF-36)
- 9. Physical evaluation for hernia recurrence
  - \*\*\*Once a subject has been diagnosed with a true hernia recurrence (either by physical exam or by CT Scan), he/she will be followed only for the planned re-operation (if indicated) and details of the etiology of the recurrence will be captured in the subject's study binder (CRF), when available. The subject will only be followed to capture information about the re-operation once a recurrence is diagnosed.
  - \*\*\*There is no need to capture implant related data or to conduct follow up visits between the diagnosis of recurrence and the operation for the recurrence. If a participant is not scheduled for a re-operation, his/her study participation will end at this point and this information will be documented on the CRF.
- 10. Clinical evidence of eventration, implant failure, implant related complications, etc. Photographs of the surgical site may be taken to document evidence of adverse events, eventration, implant failure, implant related complications, etc.
- 11. VAS

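### The primary endpoint is tied to the implant repair, so total implant removal before 1 year never counts as failure and a later hernia at the site may not qualify

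*Combined protocol and SAP*

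**What the plan says.** The objective in section 1.2 is to "compare the effectiveness of Fortiva Porcine Dermis versus Strattice Reconstructive Tissue Matrix for the underlay reinforcement of complicated ventral hernia repair". Section 2.4.1 makes the primary event a true hernia recurrence within 1 year, specified as a "true defect in the implant repair in which intra-abdominal contents are protruding through the defect".

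Section 2.4.2 lists "Implant failure requiring partial or total removal" as a separate secondary endpoint. The visit schedule expects such cases: Visits 3 to 8 (sections 6.3 to 6.8) each carry an item worded "Return to OR for additional repair or graft removal (scheduled or date of return" or equivalent. Visits 3 to 7 also include "Physical evaluation for hernia recurrence", with no exception for patients whose implant is out.

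Two provisions govern what happens to such a patient afterwards. Under section 2.3, a diagnosed recurrence ends routine follow-up: "The subject will only be followed to capture information about the re-operation once a recurrence is diagnosed". Removal is not named there. Under section 5.3.3, the investigator may withdraw a subject who "Experiences a serious or intolerable AE" or who develops a condition on the exclusion list, and section 5.3.4 allows replacement at the sponsor's discretion.

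Section 3.2 analyses patients by assigned arm and, if superiority is not shown, goes on to assess equivalence on the same outcomes. No section states whether removal or replacement of the implant before 1 year is an event, a non-event, a censoring point or missing data in the primary analysis.

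**The concern.** Total removal is a way for the implant to fail that can also prevent the primary event from being recorded. If the endpoint needs an implant repair in which to find a defect, nothing is left to qualify once the implant is out. If the site is re-repaired with other material and holds, the 12-month examination finds no recurrence, and that result belongs to the arm whose implant was taken out. Intention-to-treat does not resolve this, because it fixes the arm and not the outcome value.

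The stake is the direct comparison of two implants. An implant removed more often could look better on recurrence because of those removals. The planned equivalence step uses the same outcomes, so it would inherit the shift. The plan gives no equivalence margin against which to judge whether the shift is small.

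**Working it through.** **The plan's own figure.** Section 3.1 gives 120 patients (60 per arm), 80% power and a log-rank test, with 15 to 20% dropout. It cannot be reproduced, because no hazard, recurrence rate or hazard ratio is stated. Solving backwards at two-sided alpha 0.05 (an assumption), with events = n per arm × (p1 + p2) and HR = ln(1 − p2)/ln(1 − p1):

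- Reference 24% (low end of the primary-closure range in section 1.1), 60 per arm: p2 = 7.2%, HR 0.27, events 60 × (0.24 + 0.072) ≈ 19. With 20% dropout (48 per arm): p2 = 6.1%, HR 0.23, events ≈ 14.
- Reference 50% (top of the range in section 2.2), 60 per arm: p2 = 26.1%, HR 0.44, events 60 × (0.50 + 0.261) ≈ 46. With 20% dropout: p2 = 23.6%, HR 0.39, events ≈ 35.

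The point does not depend on these figures. They show only that the primary comparison may rest on few events.

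**Which patients are affected.**

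| Case before 1 year | Primary outcome under the current text |
|---|---|
| True recurrence diagnosed before or at removal | Already an event; not affected |
| Partial removal | Implant remains, so the definition still applies; not affected |
| Total removal, later hernia at the site | Unclear; read literally, may not qualify |
| Total removal, re-repair with other material, site holds | Not a failure: non-event or censored |
| Total removal, then withdrawn under 5.3.3 | Missing |

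**Size of the shift.** Every rate here is an assumption. Let r be the recurrence risk, equal in both arms among patients who keep the implant, and let eA and eB be the total-removal rates, with removal preceding any recurrence.

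- Removals scored as non-events: observed rate = r(1 − e), so B − A = −r(eB − eA).
- Removals scored as failures: observed rate = e + r(1 − e), so B − A = (1 − r)(eB − eA).

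Worked case, r = 20%, removal 2% vs 10%:

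- Non-event: 0.20 × 0.98 = 19.6% vs 0.20 × 0.90 = 18.0%. Arm B looks 1.6 points better.
- Failure: 2 + 19.6 = 21.6% vs 10 + 18.0 = 28.0%. Arm B is 6.4 points worse.

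Difference B − A in percentage points (non-event rule / failure rule):

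| Removal A vs B | r = 10% | r = 20% | r = 30% |
|---|---|---|---|
| 0% vs 5% | −0.5 / +4.5 | −1.0 / +4.0 | −1.5 / +3.5 |
| 2% vs 10% | −0.8 / +7.2 | −1.6 / +6.4 | −2.4 / +5.6 |
| 0% vs 10% | −1.0 / +9.0 | −2.0 / +8.0 | −3.0 / +7.0 |
| 5% vs 15% | −1.0 / +9.0 | −2.0 / +8.0 | −3.0 / +7.0 |
| 5% vs 5% | 0 / 0 | 0 / 0 | 0 / 0 |

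The non-event rule therefore favours the arm with more removals by 0.5 to 3.0 points, which is 0.3 to 1.8 patients in an arm of 60. The failure rule puts that arm 3.5 to 9.0 points behind. Censoring at removal gives no shift under these assumptions, but only if censoring is unrelated to the risk of recurrence.

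**The case against.** The strongest reply is that the damaging reading is only one reading. Section II states the primary outcome simply as hernia recurrence at 1 year. The parenthesis in 2.4.1 may be meant only to separate a true defect from the functional hernias and eventration listed in 2.4.2. Under section 2.2 the implant reinforces a primary fascial closure, so taking it out does not plainly abolish the repair, and examination for recurrence continues at later visits. Removal is also reported as its own endpoint, so an imbalance would be visible. Keeping anatomical recurrence apart from explantation is a legitimate choice.

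Most of this stands, and it limits the point. A reader might infer that any patient whose implant is removed can no longer have an event, stays in the 1-year denominator and counts as a success. The documents do not say so. Section 5.3.3 allows withdrawal, which would make the outcome missing, and a log-rank analysis could censor the patient.

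A reader might also reach a larger shift by assuming removal of 5% vs 15% and that half of the removed patients would have recurred: 0.5 × 10 = 5.0 points. That needs a threefold imbalance that nothing in the documents suggests, and a recurrence risk at the very top of the 18 to 50 percent range quoted in section 2.2.

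The reply does not supply the missing rule. Every route left open keeps a total removal that is re-repaired and holds out of the primary failure count, and the wording can be used to exclude a hernia found after total removal. A separate removal endpoint shows the imbalance but does not correct the primary comparison.

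**Conclusion.** The point holds for total removal, or re-repair with other material, before 1 year without a prior true recurrence. For these patients the primary endpoint records no failure, and whether a later hernia at the site counts is left to interpretation. Partial removal and removal at a diagnosed recurrence are outside it.

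Any bias between arms requires unequal removal rates, and the documents give none. Under the assumed rates, the shift when removals are scored as non-events is 0.5 to 3.0 percentage points in favour of the implant removed more often, and zero if rates are equal. That is modest, and it does not show that the trial would reach the wrong conclusion. It still deserves correction, because the same outcomes feed the equivalence assessment, the event count may be low, and the choice of rule can reverse the sign of the difference (1.6 points better against 6.4 points worse in the worked case).

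**What to change.** In section 2.4.1, define the event as a defect at the index repair site with protruding intra-abdominal contents, whether or not the study implant is still in place. A hernia found after total removal or re-repair then counts in the assigned arm.

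In section 3.2, add one pre-specified sensitivity analysis of the primary endpoint, in all randomised patients by assigned arm, in which total implant removal or re-repair with other material at or before the 12-month visit counts as failure. This covers the patient whose re-repair holds. It also covers the patient withdrawn after removal, provided the removal was recorded.

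The cost is one change of definition and one extra analysis, using removal and re-operation data the visits already collect. The downside is that the sensitivity endpoint mixes recurrence with removal, which may happen for other reasons. It should be reported beside the primary result and should not replace it.
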